9.7. Warnings and Precautions

Special warnings or precautions for the study drug, derived from safety information collected by the sponsor or its designee, are presented in the [IB](#). Additional safety information collected between IB updates will be communicated in the form of Investigator Notifications. Any important new safety information should be discussed with the participant during the study, as necessary. If new significant risks are identified, they will be added to the ICF.

9.8. Product Complaints

The sponsor collects product complaints on study drugs and drug delivery systems used in clinical studies in order to ensure the safety of study participants, monitor quality, and facilitate process and product improvements.

All product complaints associated with material packaged, labeled, and released by the sponsor or its designee will be reported to the sponsor. All product complaints associated with other study material will be reported directly to the respective manufacturer.

The investigator or his/her designee is responsible for reporting a complete description of the product complaint via email or other written communication to the sponsor contact or respective manufacturer as noted in the packaging information. Any AE associated with a product complaint should be recorded as described in Section [9.3](#).

If the investigator is asked to return the product for investigation, he/she will return a copy of the product complaint communication with the product.

9.9. Treatment of Overdose

For this study, any dose of study treatment greater than 600 mg within a 24-hour time period will be considered an overdose.

Incyte does not recommend specific treatment for an overdose.

In the event of an overdose, the investigator should:

- Contact the medical monitor immediately.
- Closely monitor the participant for any AE/SAE and laboratory abnormalities.
- Obtain a plasma sample for PK analysis within 2 days from the date of the last dose of study treatment if requested by the medical monitor (determined on a case-by-case basis).
- Document the quantity of the excess dose as well as the duration of the overdose in the eCRF.

Decisions regarding dose interruptions or modifications will be made by the investigator in consultation with the medical monitor based on the clinical evaluation of the participant.

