2.2.1. Justification of Itacitinib Dose

As mentioned above, in participants with aGVHD receiving itacitinib 200 mg QD, with dose reduction to 100 mg QD in some participants on a strong CYP3A inhibitor, in combination with corticosteroids, the Day 28 ORR was not statistically different than placebo in combination with corticosteroids. However, at this dose the safety profile was consistent with that previously observed with no new safety signals. A preliminary exposure/response analysis demonstrated a statistically significant relationship between steady-state exposure and Day 28 ORR with response rates in participants in the upper tertile of exposure (ie, $> \sim 6500 \text{ nM}\cdot\text{h}$) predicted to be $> 90\%$, well above the response rate with corticosteroids alone. In study INCB 39110-309, a randomized, double-blind, placebo-controlled, Phase 3 study evaluating itacitinib or placebo in combination with corticosteroids as a first-line treatment for participants with cGVHD, preliminary data revealed that in participants with relatively high exposures ($> 20 \mu\text{M}\cdot\text{h}$), Grade 3/4 AEs, mainly thrombocytopenia, were manageable with dose reductions and/or discontinuations. Itacitinib doses as high as 400 mg BID and 600 mg QD have been studied in other patient populations (eg, rheumatoid arthritis, plaque psoriasis, and myelofibrosis) and were well tolerated with manageable AEs that were not prohibitive to dosing. Approximately 10% of participants with aGVHD receiving 200 mg QD had predose concentrations that were below the limit of quantification, suggesting inhibition of the target (ie, JAK1) was not maintained throughout the dosing interval. Considering the disease pathology of BOS relative to aGVHD and cGVHD, the dose range and corresponding safety profile across these populations and other autoimmune and oncology populations, and response rates observed in participants with aGVHD and cGVHD, doses of 400 mg QD, 600 mg QD, and 300 mg BID were selected for this Phase 2 dose-ranging study in BOS patients. These doses should be adjusted to maintain a consistent exposure with concomitant use of a strong CYP3A inhibitor; see Section 2.2.2.

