2.2.2. Dose Modifications for Concomitant Medications

Observed preliminary data from study INCB 39110-301 suggested that exposures are similar between participants with aGVHD either not on a CYP3A inhibitor or on a weak or moderate CYP3A inhibitor; and exposures are similar between participants with aGVHD on various CYP3A inhibitors, mainly posaconazole or voriconazole. Using a preliminary population PK model, the impact of a strong CYP3A inhibitor on exposure was characterized, and simulations were performed to identify a dose reduction such that exposures remain generally consistent when an individual is receiving a strong CYP3A inhibitor and when he/she is not.

From [Table 5](#), it is recommended that the dose be adjusted as follows:

- If on 400 mg QD, dose adjust to 300 mg QD with concomitant administration of a strong CYP3A inhibitor (eg, posaconazole, voriconazole, itraconazole, or ketoconazole).
- If on 600 mg QD, dose adjust to 400 mg QD with concomitant administration of a strong CYP3A inhibitor.
- If on 300 mg BID, dose adjust to 200 mg BID with concomitant administration of a strong CYP3A inhibitor.

Table 5: Simulated Itacitinib Daily Exposure By Dose and Concomitant Strong CYP3A Inhibitor Administration

Itacitinib Dose	Daily AUC (nM·h) Without Concomitant Strong CYP3A Inhibitor Use	Daily AUC (nM·h) With Concomitant Strong CYP3A Inhibitor Use
200 mg QD	4220	6720
300 mg QD	7740	12,700
400 mg QD	11,400	18,300
600 mg QD	19,000	31,200
200 mg BID	8120	12,800
300 mg BID	15,000	24,300

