The assigned dose level (Dose Level 1, 2, or 3) will determine the dose and schedule of itacitinib to be administered as the starting dose as well as any subsequent reductions in dose that may occur due to toxicity. The dose administered will also be determined based on whether the participant is taking a concomitant strong CYP3A inhibitor (eg, voriconazole, itraconazole, posaconazole, ketoconazole; see [Appendix C](#)). **Participants who are not taking concomitant strong CYP3A inhibitor will be administered the dose specified in Column A of Table 9. Participants who are taking concomitant strong CYP3A inhibitor will be administered the dose specified in Column B of Table 9.** If a participant begins taking or discontinues a strong CYP3A inhibitor during treatment, the dose should be adjusted accordingly per [Table 9](#) (eg, if the participant begins taking a strong CYP3A inhibitor, he/she should be switched to the dose specified in Column B). At the time of either addition or discontinuation of a strong CYP3A inhibitor, close monitoring of CNI levels should be undertaken to ensure safety of the study participant.

Participants enrolled before Protocol Amendment 2 who were randomized to receive the 200 mg QD dose and who are ongoing at the time of amendment approval may increase their itacitinib dose to Dose Level 2 using the same parameters outlined in [Table 9](#), with approval from the sponsor. Participants must have tolerated the 200 mg QD dose and have not experienced any AEs \geq Grade 3 that are considered related to itacitinib. Additionally, the participant must agree to weekly clinic visits for a targeted physical examination and hematology/complete blood count assessment for the first 2 weeks after the dose increase.

Participants may have dose reductions or modifications during the course of treatment based on AEs, clinical evaluation, changes to concomitant medications, and laboratory assessments. Dose modifications of itacitinib for toxicity should follow the algorithm outlined for each dose level in [Table 9](#). See Section [6.2.1](#) for criteria and guidelines related to itacitinib dose modifications due to AEs and Section [6.3](#) for guidelines related to itacitinib dose modifications due to select concomitant medications.

Participants are permitted to remain on itacitinib treatment until withdrawal from study treatment is considered necessary as per Section [7.1.1](#).

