6.2. Dose Modifications

6.2.1. Criteria and Procedures for Dose Interruptions of Study Drug

Safety concerns should be discussed with the sponsor immediately upon occurrence or awareness to determine if the participant should continue or discontinue study treatment.

Treatment with itacitinib may be delayed up to 14 days to allow for resolution of toxicity. After interruption, participants should be evaluated on a weekly basis until resolution/improvement of the AE. Participants may resume treatment if no medical condition or other circumstance exists that, in the opinion of the investigator, would make the participant unsuitable for further participation in the study. The investigator should contact the medical monitor to discuss the case of any participant whose treatment has been delayed for more than 14 days before restarting treatment.

Because participants may enter the study with extensive comorbidities, dose reduction recommendations in [Table 10](#) are provided as guidelines. Each participant may undergo up to 2 dose reductions for toxicity. Individual decisions regarding dose modifications should be made using clinical judgment and an individual benefit/risk assessment taking into account relatedness of the AE to the study drug and the participant's underlying condition. Adverse events that have a clear alternative explanation, or transient (≤ 72 hours) abnormal laboratory values without associated clinically significant signs or symptoms, may be exempt from dose modification rules. The sponsor's medical monitor may be consulted for advice.

Table 10: Guidelines and Procedures for Interruption of Study Drug

ADVERSE EVENT	ACTION TAKEN
Chemistry	

• AST and/or ALT is $> 3.0 \times \text{ULN}$	
Step 1: Interrupt itacitinib administration up to 14 days until the toxicity has resolved to \leq Grade 1. Exceptions require sponsor approval.
 
Step 2: Restart itacitinib at previous dose. If assessed as related to itacitinib, restart at reduced dose level and monitor as clinically indicated.

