9.1. Definition of Adverse Event

Adverse Event Definition

• An AE is any untoward medical occurrence associated with the use of a drug in humans, whether or not considered drug-related.• An AE can therefore be any unfavorable and unintended sign (including an abnormal laboratory finding), symptom, or disease (new or exacerbated) temporally associated with the use of study treatment.
Events Meeting the Adverse Event Definition

• Any safety assessments (eg, ECG, vital signs measurements), including those that worsen from baseline, considered clinically significant in the medical and scientific judgment of the investigator (ie, not related to progression of underlying disease).• Abnormal laboratory test results constitute an AE if they are considered clinically meaningful, induce clinical signs or symptoms, require concomitant therapy, or require changes in study drug. Whenever possible, a diagnosis (eg, anemia, thrombocytopenia) should be recorded in the eCRF rather than the abnormal lab result (eg, low hemoglobin, platelet count decreased).• Exacerbation of a chronic or intermittent pre-existing condition including either an increase in frequency and/or intensity of the condition.• New conditions detected or diagnosed after study treatment administration even though they may have been present before the start of the study.• Signs, symptoms, or the clinical sequelae of a suspected drug-drug interaction.• Signs, symptoms, or the clinical sequelae of a suspected overdose of either study treatment or a concomitant medication. Overdose per se will not be reported as an AE/SAE unless it is an intentional overdose taken with possible suicidal/self-harming intent. Such overdoses should be reported regardless of sequelae.
Events NOT Meeting the Adverse Event Definition

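### Section 9.9 applies one 600 mg overdose limit to everyone, so 600 mg/day on a strong CYP3A inhibitor, above the 400 mg/day maximum in Table 9, is not an overdose

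*Protocol*

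**What the plan says.** Protocol Section 9.9 sets a single limit: "any dose of study treatment greater than 600 mg within a 24-hour time period will be considered an overdose". It does not mention concomitant inhibitors. Four actions depend on it: immediate contact with the medical monitor, close monitoring for AEs and laboratory abnormalities, a PK sample if the monitor asks for one, and an eCRF record of the size and duration of the excess.

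Elsewhere the dose depends on inhibitor use. Section 2.2.2 reports that "simulations were performed to identify a dose reduction such that exposures remain generally consistent when an individual is receiving a strong CYP3A inhibitor", and gives as one result: "If on 600 mg QD, dose adjust to 400 mg QD with concomitant administration of a strong CYP3A inhibitor". Table 9 carries this through as Column A (no inhibitor) and Column B (inhibitor). Section 6.1 adds: "If a participant begins taking or discontinues a strong CYP3A inhibitor during treatment, the dose should be adjusted accordingly". Section 6.3.1.2 repeats this for azoles. Section 6.3.3 points the other way: it lists strong inhibitors among medications not to be initiated on study and requires that they began more than 4 weeks before first dose.

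On reporting, Section 9.1 says: "Overdose per se will not be reported as an AE/SAE unless it is an intentional overdose taken with possible suicidal/self-harming intent".

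**The concern.** The limit is in milligrams, while the dosing scheme aims at similar exposure. Without an inhibitor, 600 mg/day is the top assigned dose and anything above it is flagged. With an inhibitor the top assigned dose is 400 mg/day, but nothing is flagged until the total exceeds 600 mg. The range between 400 and 600 mg/day is the one the dose adjustment is meant to avoid, and the overdose rule does not reach it.

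At stake are notification, monitoring and documentation. A site that discovers such an error has no Section 9.9 duty to call the medical monitor or record the excess. If there are no sequelae, an accidental excess is not an AE either.

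**Working it through.** **Inputs.** Table 9 gives the assigned doses; Table 5 gives simulated daily AUC in nM·h:

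| Regimen | With inhibitor | Without inhibitor |
|---|---|---|
| 600 mg QD | 31,200 | 19,000 |
| 300 mg BID | 24,300 | 15,000 |
| 400 mg QD | 18,300 | 11,400 |
| 200 mg BID | 12,800 | 8,120 |
| 300 mg QD | 12,700 | 7,740 |
| 200 mg QD | 6,720 | 4,220 |

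**1. Where 600 mg sits.** The highest daily dose in Column A is max(2×300, 400, 600) = 600 mg, which equals the Section 9.9 limit. The highest in Column B is max(2×200, 300, 400) = 400 mg. The limit is 600/400 = 1.5 times the Column B maximum.

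**2. Highest planned starting exposure.** Take each starting dose in its own column. Column A gives 15,000 (300 mg BID), 11,400 (400 mg QD) and 19,000 (600 mg QD). Column B gives 12,800 (200 mg BID), 12,700 (300 mg QD) and 18,300 (400 mg QD). The maximum is 19,000.

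**3. Unflagged exposures on an inhibitor.** Both regimens total exactly 600 mg, and 600 is not greater than 600.
- 600 mg QD: 31,200/19,000 = 1.64
- 300 mg BID: 24,300/19,000 = 1.28

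**4. Routes to 600 mg on an inhibitor.**
- *Missed switch to Column B at the starting dose.* Against the dose that should have been given, Dose Level 3 is 31,200/18,300 = 1.70 and Dose Level 1 is 24,300/12,800 = 1.90. Dose Level 2 is 18,300/12,700 = 1.44, but 18,300 is below 19,000. Of the nine Column A cells, only the Dose Level 1 and 3 starts exceed 19,000 when left unswitched.
- *Doubling Column B 300 mg QD* (Dose Level 2 start, Dose Level 3 first reduction): 31,200/12,700 = 2.46. Doubling stays at or below 600 mg in 11 of the 18 Table 9 cells, but only these two exceed 19,000.
- *An extra 200 mg on Column B 200 mg BID* (Dose Level 1 start) totals 600 mg. Table 5 has no value for this. Assuming simple addition, three separate 200 mg doses give 12,800×1.5 = 19,200. If the extra is taken together with a scheduled dose, the total is 18,300 + 12,800/2 = 24,700. The range is 1.01 to 1.30 times 19,000.

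**5. With a limit of more than 400 mg on an inhibitor.** All the routes above that exceed 19,000 are flagged. The largest unflagged sustained exposure on an inhibitor falls from 31,200 to 18,300, and no Column B daily total exceeds the limit.

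**The case against.** The strongest reply is that other provisions already cover a missed switch or extra tablets. Section 6.1 requires the switch and close CNI monitoring. Table 2 schedules concomitant-medication review at every treatment visit. Section 6.4 requires pill counts. Compliance is calculated (Section 6.6, SAP 6.5) and deviations are listed (SAP 6.3). Hematology is scheduled throughout treatment, and the Table 10 platelet rules apply whatever the cause. Section 6.2.1 adds: "Safety concerns should be discussed with the sponsor immediately upon occurrence or awareness". These help to find an error, record it afterwards or respond to toxicity, so it would be wrong to infer that participants are unprotected. None of them requires the immediate contact and excess-dose record of Section 9.9 once a 600 mg day on an inhibitor is known. Section 6.2.1 depends on the investigator seeing a safety concern in a dose that the protocol does not call an overdose.

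A second reply is that Section 6.3.3 restricts on-study inhibitor starts, so a missed switch should be rare. That stands as a limit on frequency. Sections 6.1 and 6.3.1.2 nevertheless give instructions for such starts, and the extra-dose routes need no new inhibitor.

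A third reply concerns tolerability. A reader might take the 20 µM·h in Section 2.2.1 as a safety ceiling that 31.2 and 24.3 µM·h breach. The text does not support that: it says that at such exposures in the cGVHD study "Grade 3/4 AEs, mainly thrombocytopenia, were manageable with dose reductions and/or discontinuations". It also says "Itacitinib doses as high as 400 mg BID and 600 mg QD have been studied in other patient populations" and describes them as well tolerated, without stating inhibitor use. If 400 mg BID without an inhibitor scales like the other BID rows (0.96 to 0.97 of twice the QD value, so about 22,000), then 24,300 is only about 1.1 times a regimen reported as tolerated. This weakens any claim of harm, especially at Dose Level 1. It does not explain the limit, because Section 9.9 itself classes 400 mg BID (800 mg) as an overdose.

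**Conclusion.** The gap is real but narrow. The overdose definition follows the maximum dose without an inhibitor and was not lowered where the protocol lowers the dose. It leaves unflagged simulated exposures of 1.64 (600 mg QD) and 1.28 (300 mg BID) times the highest planned starting exposure.

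The ratios rest on Table 5: one simulated value per regimen, from a preliminary population PK model, with no spread given. They fit a sustained error and only approximate a single extra dose.

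Two broader readings fail. A missed switch is not a problem at every dose level, since at Dose Level 2 it stays within planned exposure. Nor does the trial's evidence suffer, because no endpoint or analysis depends on the overdose definition. A changed definition also cannot detect an error the site does not know about; it only sets what follows once the site knows. Enrollment is closed and Phase 2 was dropped (Section 2.3, Appendix E), so only participants still on treatment are affected. Priority is low; the change is worth making because it is cheap.

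**What to change.** Keep the Section 9.9 sentence, including its 24-hour wording, and add:

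*For participants taking a strong CYP3A inhibitor that requires Column B dosing (Table 9), more than 400 mg in any 24-hour period is also an overdose. For this 400 mg limit, assigned doses taken within the permitted 8-hour window, and assigned doses taken on the day of a switch between Columns A and B, do not by themselves count as an overdose.*

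The carve-out is needed for two reasons. Table 8 allows a dose up to 8 hours late, so a late 300 mg QD dose followed by an on-time one gives 600 mg in about 16 hours. At Dose Level 1, a switch day can hold 300 mg in the morning and 200 mg in the evening, 500 mg in all, with both doses as assigned. Because the 600 mg sentence stays, nothing flagged today is lost.

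The cost is a few more medical-monitor contacts and eCRF entries, with no new visits or analyses. Excess doses within planned exposure in dose-reduced participants stay unflagged. Relative to the assigned dose these reach 18,300/6,720 = 2.72 on an inhibitor (400 instead of 200 mg QD) and 19,000/4,220 = 4.50 without one (600 instead of 200 mg QD).

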10. STATISTICS

10.1. Sample Size Determination

10.1.1. Phase 1

In Phase 1, approximately 24 participants will be enrolled to participate across the 3 dose levels of itacitinib (see [Table 9](#)) to identify the RP2D. A sample size of 24 participants (8 per dose level) allows for concurrent enrollment at 3 dose levels that have been previously characterized in other disease settings and is expected to enable the clinical characterization of safety and efficacy. No formal statistical comparison will be performed between treatment groups.

10.1.2. Phase 2

The FEV₁ response rate for itacitinib is assumed to be 20%. In order for the lower confidence limit of the 95% CI to exclude 5%, approximately 55 participants are needed.

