10.3. Level of Significance

No formal efficacy hypotheses will be tested. All CIs will be 95%.

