10.4. Statistical Analyses

10.4.1. Primary Analysis

The primary endpoint is FEV₁ response rate through the Week 12 visit, defined as the proportion of participants demonstrating a $\geq 10\%$ absolute increase in FEV₁ compared to baseline. The primary analysis will be conducted once the last participant completes the Week 12 visit or withdraws from the study. If a participant withdraws from the study before Week 12, or there is no FEV₁ data up to and including Week 12, then the participant will be considered a nonresponder.

Summary statistics and 95% CI will be provided.

Primary efficacy analysis will be conducted for the full analysis data set.

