# 3.2. Control of Type I Error

No formal efficacy hypotheses will be tested, and no alpha control will be implemented.

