### 7.3. Analysis of the Primary Efficacy Parameter

In Phase 1, the primary endpoint is FEV1. Change and percentage change from baseline in FEV1 and FEV1 % predicted will be summarized by visit and treatment group.

In Phase 2, the primary endpoint is  $FEV_1$  response rate through the Week 12 visit, defined as the proportion of participants demonstrating a  $\geq 10\%$  absolute increase in  $FEV_1$  compared with baseline, confirmed by 2 consecutive spirometric assessments  $\geq 1$  week apart. The primary analysis will be conducted once the last participant completes the Week 12 visit or withdraws from the study. If a participant withdraws from the study before Week 12, or there is no  $FEV_1$  data up to and including Week 12, the participant will be considered as a nonresponder. Summary statistics and 95% CIs will be provided. Confidence intervals will be calculated based on the exact method for binomial distributions.

In Phase 1,  $FEV_1$  response rate will also be calculated due to the fact that duration of  $FEV_1$  response is a secondary efficacy endpoint in Phase 1.

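### Is the Phase 2 size of 55 the wrong number for an exact 95% confidence interval that excludes 5%?

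*Protocol*

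**What the plan says.** Protocol section 10.1.2 assumes a response rate of 20% for itacitinib in Phase 2 and then says: "In order for the lower confidence limit of the 95% CI to exclude 5%, approximately 55 participants are needed". SAP section 3.3 carries the same statement. Neither place attaches a probability to it or names the type of interval used for sizing.

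Other sections bear on how to read it:

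- Protocol section 10.3 sets all intervals at the 95% level.
- SAP section 7.3 fixes the method for the primary endpoint: "Confidence intervals will be calculated based on the exact method for binomial distributions".
- SAP section 3.2 rules out a test: "No formal efficacy hypotheses will be tested, and no alpha control will be implemented".
- Protocol section 10.4.1 deals with missing outcomes. "If a participant withdraws from the study before Week 12, or there is no FEV₁ data up to and including Week 12", the participant counts as a nonresponder. No inflation for dropout is mentioned.
- The Protocol Summary gives about 55 as an upper bound on Phase 2 enrolment.
- Protocol section 2.3 records that the sponsor decided not to go on to Phase 2.

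**The concern.** Read literally, with no probability attached, the sentence says that 55 participants are what it takes for an observed 20% to exclude 5%. That is not so under the exact interval, where 4 responders among 20 are already enough. Read as a power statement at the customary 80%, the exact method again needs far fewer than 55. The familiar formula that lands near 55 uses the Wald variance, which is not the planned method of analysis. It is natural to suspect that the size was worked out for one interval and the analysis written for another.

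If so, the only justification given for the Phase 2 size would not describe the planned analysis. A reader also could not see that 7 of 55 responders (12.7%), well below the assumed 20%, would clear the 5% mark.

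**Working it through.** **Inputs.** Assumed true rate p1 = 0.20, rate to exclude p0 = 0.05, stated n = 55 (Protocol 10.1.2, SAP 3.3). Level 95% (Protocol 10.3), taken as two-sided because sidedness is not stated. Exact (Clopper-Pearson) interval (SAP 7.3). Power is not stated, so 80%, 90% and 95% are tried as assumptions.

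**Reproducing the plan's figure with a Wald formula.** n = (z₀.₉₇₅ + z_power)² × p1(1 − p1) / (p1 − p0)². At 80% power this is (1.960 + 0.842)² × 0.16 / 0.0225 = 55.8, so 56 after rounding up. At n = 55 the same formula gives 79.4% power. This is close to the stated figure.

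**Exact method, if 20% is observed.** 4/20 has a lower limit of 5.7%, which excludes 5%. 11/55 has an interval of 10.4% to 33.0%.

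**Exact method, as a probability.** For each n, find the smallest count r whose lower limit exceeds 5%, then compute P(X ≥ r) for X ~ Binomial(n, 0.20). Because r moves in steps, the probability is not monotone in n. The table therefore shows where each level is first reached and where it holds for every larger n.

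| Probability | First reached | Holds from |
|---|---|---|
| 80% | n = 33 (r = 5, 81.8%) | n = 39 (r = 6, 82.0%) |
| 90% | n = 45 (r = 6, 91.0%) | n = 51 (r = 7, 90.8%) |
| 95% | n = 57 (r = 7, 95.5%) | n = 63 (r = 8, 95.3%) |

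**At n = 55.** 6/55 has a lower limit of 4.1% and does not exclude 5%. 7/55 has an interval of 5.3% to 24.5% and does. So r = 7, and P(X ≥ 7) is 94.2% at a true 20% and 1.9% at a true 5%. The neighbouring sizes give 94.9% (n = 56) and 95.5% (n = 57).

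**Other routes to a number near 55.** A Wald interval with continuity correction, with power computed from the binomial, reaches 80% at n = 56. The 80% Wald formula is therefore not the only derivation that fits. The exact method at about 95% power also comes within 2 participants of 55.

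**Effect of counting withdrawals as nonresponders.** The documents give no withdrawal rate, so take 10% and 20% as illustrations, with everyone else responding at 20%. The effective rates are 0.9 × 20% = 18% and 0.8 × 20% = 16%. P(X ≥ 7) with n = 55 is then 88.8% and 79.8%.

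**The case for a change.** The strongest case for a change is that this sentence is the only support for the Phase 2 size and that, with no test planned, excluding 5% is the only numerical benchmark for Phase 2 efficacy. Read literally the sentence is inexact, and 55 is not the smallest exact-method size for an observed 20%, nor for 80%, 90% or 95% probability. SAP Amendment 1 came after the decision to stop before Phase 2 and still carries the statement. One added sentence giving the probability, the count of 7 and the expected interval would make it traceable at almost no cost.

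Much of this stands as description: the power and the sizing method are missing, and the literal reading fails. The stronger inference does not stand. To call 55 the wrong number, or 16 more than needed (55 − 39), one must assume an 80% target that appears in neither document. Reading the figure as a Wald calculation is a guess from a near match, and a 95% exact design is about as near. The 16 are not shown to be surplus either: under the nonresponder rule, a 20% withdrawal rate would bring the exact probability at 55 down to about 80%.

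That 7 of 55 lies below the assumed 20% is not a defect. In any adequately powered design that sets 5% against 20%, the smallest passing proportion falls between the two rates. The plan also sets no success rule for Phase 2, so the count of 7 is a derived property of the interval and not a hidden criterion.

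**Conclusion.** The figure of 55 is not shown to be wrong. It agrees to within 2 participants with an 80% Wald calculation (56) and with the SAP's own exact method at about 95% power (57). The documents cannot settle which was used. Under the planned interval, 55 participants give a 94.2% chance that the lower limit exceeds 5% at a true 20%, so any discrepancy errs on the side of more information than the sentence promises.

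The gap is a missing power statement, and an analyst can fill it directly from the binomial distribution. Stating it would leave the enrolment ceiling, the exact interval and the interpretation as they are. Phase 2 was not opened, so no data will be analysed against this size. The conclusion rests on a two-sided 95% exact interval and a true rate of 20% with withdrawals already included in that rate. If withdrawals come on top of it, the probability falls as shown above, which makes 55 look less generous, not mistaken.
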